9.2.3 Case Report Forms

All data generated by the site personnel will be captured electronically at each study center using eCRFs. Data from external sources (such as laboratory data) will be imported/entered into the database. Case reports forms must be kept current to reflect patient status at each phase during the course of trial. Patients are not to be identified on the case report form by name. Appropriate coded identification (e.g. Subject Number) and Patients initials must be used. The investigator must make a separate confidential record of these details (subject identification code list) to permit identification of all patients enrolled in a clinical trial in case follow-up is required. Relevant medical history will be documented at the screening visit. Thereafter during the trial narrative statements relative to the patient's progress during the trial will be maintained. See also 9.2.4. The investigator will be responsible for retaining all records pertaining to the trial as specified in the agreement.

9.2.4 Source documents

Source documents provide evidence for the existence of the patient and substantiate the integrity of the data collected. Source documents are filed at the investigator's site. Data reported on the Case Report Forms that are derived from source documents must be consistent with the source documents or the discrepancies must be explained. The investigator may need to request previous medical records or transfer records, depending on the trial; also current medical records – not just shadow charts – must be available. The following data to be reported on the eCRF should be included and derived from the source documents:

- Patient identification (initials, gender, data of birth/age)
- Patient participation in the trial (drug, trial number, subject number, date informed consent given)
- Dates of Patient's visits
- Medical history
- Medication history
- AE onset and end
- SAE onset and end
- Originals or copies of laboratory results
- Originals or copies of ultrasound findings or MRI findings or FibroScan® findings and other results if applicable.
- Conclusion of patient's participation in the trial.

9.2.5 Direct Access to Source Data / Documents

Approved by: [name]	Protocol No. SARO.17.009 Version No.: 5.0
------------------------------------	--

 Zydus Discovery DMCC	CLINICAL TRIAL PROTOCOL Saroglitzaz Magnesium – Phase 2A SARO.17.009	Confidential Page 69 of 82
---	--	-------------------------------

The Investigator/ institution will permit trial-related monitoring, audits, IRB / IEC review and regulatory inspection, providing direct access to all related source data / documents. Case report forms and all source documents, including progress notes and copies of laboratory and medical test results must be available at all times for review by the Sponsor's clinical trial monitor and inspection by health authorities (e.g., FDA, or other applicable regulatory authorities). The on-site monitor will review all eCRFs, and written informed consents. The accuracy of the data will be verified by reviewing the documents described in Section 9.2.4.

9.2.6 Trial Monitoring

It is the responsibility of the Investigator to ensure that the study is conducted in accordance with the protocol, ICH GCP, and applicable regulatory requirements, and that valid data are entered into the eCRFs. To achieve this objective, the study monitor's duties are to aid the Investigator and, at the same time, the Sponsor in the maintenance of complete, legible, well organized and easily retrievable data. Before the enrollment of any patient in this study, the Sponsor or their designees will review with the Investigator and site personnel the following documents: protocol, Investigator's Brochure, eCRFs and procedures for their completion, informed consent process, and the procedure for reporting SAEs. The Investigator will permit the Sponsor or their designees to monitor the study as frequently as deemed necessary to determine that data recording and protocol adherence are satisfactory. During the monitoring visits, information recorded on the eCRFs will be verified against source documents and requests for clarification or correction may be made. After the eCRF data is entered by the site, the Monitor will review the data for safety information, completeness, accuracy, and logical consistency. Computer programs that identify data inconsistencies may be used to help monitor the clinical study. If necessary, requests for clarification or correction will be sent to Investigators. The Investigator and his/her staff will be expected to cooperate with the monitor and provide any missing information, whenever possible.

9.2.7 Query Handling and Error Management

If there are any discrepancies/errors/corrections are needed in the data entered in the eCRF then the responsible monitor or data manager will raise a query in the electronic data capture application. The designee staff at the study site will answer queries sent to the investigator. This process will be continued till the discrepancies/errors are adequately resolved.

9.3 QUALITY CONTROL AND QUALITY ASSURANCE AUDIT

A quality assurance audit of this trial may be conducted by the sponsor or sponsor's designee. The quality assurance auditor will have access to all medical records, the investigator's trial related files and correspondence, and the informed consent form documentation that is relevant to this clinical trial.

Approved by: [name]	Protocol No. SARO.17.009 Version No.: 5.0
------------------------------------	--

 Zydus Discovery DMCC	CLINICAL TRIAL PROTOCOL Saroglitazar Magnesium – Phase 2A SARO.17.009	Confidential Page 70 of 82
--	---	-------------------------------

9.4 PROCEDURES

9.4.1 Adverse Events

Adverse event reporting will begin after the informed consent has been signed and will continue until end of the study (i.e., the safety telephone call). The Common Terminology Criteria for Adverse Event (Version 4.03 or higher) system will be used for reporting and grading AEs.

9.4.1.1 Definitions

An AE is any unfavorable or unintended sign, symptom or disease temporally associated with the use of study drug whether or not considered related to study drug. Adverse events may include:

- Objective signs observed by the PI or study personnel
- Subjective or objective signs/symptoms
- Concomitant disease or accidents
- Clinically relevant adverse changes in laboratory parameters observed in a patient in the course of a clinical study
- Pre-existing conditions that worsen in severity or frequency or have new signs/symptoms associated with them

Findings related to abnormal laboratory values, ECGs and vital signs, which are not considered clinically significant, are not to be recorded on the AE reporting page; such events should instead be entered in the relevant eCRF page.

9.4.1.2 Treatment-emergent Adverse Events

Treatment-emergent AEs are defined as any AE that started after the first dose of study drug or started before the first dose but increased in severity or frequency after administration of the initial dose of study drug.

9.4.1.3 Collection of Adverse Events

It is the responsibilities of the PI to collect all AEs (both serious and nonserious) derived by spontaneous, unsolicited reports of patients, by observation and by routine open questionings, e.g., "How have you felt since I last saw you?"

9.4.1.4 Assessment of Adverse Events

Each AE will be assessed by the PI with regard to the following categories:

Severity

Approved by: [name]	Protocol No. SARO.17.009 Version No.: 5.0
------------------------------------	--

 Zydus Discovery DMCC	CLINICAL TRIAL PROTOCOL Saroglitzaz Magnesium – Phase 2A SARO.17.009	Confidential Page 71 of 82
---	--	-------------------------------

The PI will provide an assessment of the severity of each AE by recording a severity rating on the appropriate AE reporting page of the patient's eCRF. Severity will be assessed according to the following scale:

Mild: Event is usually transient and easily tolerated, requiring no special treatment and causing no disruption of the patient's normal daily activities.

Moderate: Event introduces a low level of inconvenience or concern to the patient and may interfere with daily activities, but is usually improved by simple therapeutic measures. Moderate experiences may cause some interference with functioning.

Severe: Event interrupts the patient's normal daily activities and generally requires systemic drug therapy or other treatment. Severe events are usually incapacitating.

Causality

For all AEs, the PI will provide an assessment of causal relationship to study drug. The causality assessment must be recorded on the appropriate AE reporting page of the patient's eCRF.

Causal relationship will be classified according to the following criteria:

- Unrelated
- Possibly related: Suggests that the association of the AE with the study drug is unknown. However, the AE is not reasonably supported by other conditions.
- Probably related: Suggests that a reasonable temporal sequence of the AE with study drug administration exists and, based upon the PI's clinical experience, the association of the AE with study drug seems likely.
- Definitely related: Suggests that a causal relationship exists between the study drug and the AE, and other conditions (concomitant illness, progression or expression of the disease state, reaction to concomitant medication) do not appear to explain the AE.
- Unknown

Outcome

Outcome of AEs will be defined according to the ICH topic E2B, ICH Guideline, as follows:

- Recovered/Resolved
- Recovered/Resolved with sequelae
- Recovering/Resolving
- Not Recovered/Not Resolved
- Fatal
- Unknown

9.4.1.5 Recording Adverse Events

Approved by: [name]	Protocol No. SARO.17.009 Version No.: 5.0
------------------------------------	--

 Zydus Discovery DMCC	CLINICAL TRIAL PROTOCOL Saroglitazar Magnesium – Phase 2A SARO.17.009	Confidential Page 72 of 82
---	---	-------------------------------

All AEs must be recorded on the appropriate AE eCRF for the patient. All AEs must be reported whether or not considered causally related to study drug. For every AE, the PI will provide an assessment of the severity and causal relationship to study drug, will document all actions taken with regard to study drug, and will document any other treatment measures for the AE. If an outcome for an AE is not available at the time of the initial report, follow-up will proceed until an outcome is known.

9.4.1.6 Follow-up of Adverse Events

All AEs experienced by a patient, irrespective of the suspected causality, will be monitored until the AE has resolved, any abnormal laboratory values have returned to baseline or stabilized at a level acceptable to the Investigator and Medical Monitor, until there is a satisfactory explanation for the changes observed, until the patient is lost to follow-up or until the patient has died.

9.4.2 Serious Adverse Event

An SAE is an event that:

- Results in death;
- Is life threatening;
- Results in persistent or significant disability/incapacity;
- Results in inpatient hospitalization or prolongs an existing inpatient hospitalization;
- Is a congenital anomaly/birth defect;
- Is another important medical event that may not result in death, be life threatening, or require hospitalization may be considered serious when, based upon appropriate medical judgment, they may jeopardize the patient or subject and may require medical or surgical intervention to prevent one of the outcomes listed above.

Serious AEs also include events that are medically significant in the PI's judgment, including medically significant laboratory abnormalities, such as those that warrant stopping study drug for individual patients as specified in Section 4.5 of the protocol. In general, medically significant events require medical/surgical intervention to prevent one of the outcomes listed above.

[figure not shown]

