4.5 STOPPING CRITERIA FOR INDIVIDUAL PATIENTS

The following clinical events warrant discontinuation of study drug; however, the patient will continue to be followed for safety, hormonal profile, liver function tests and lipid levels until the event has resolved, i.e., clinical laboratory value(s) has/have returned to baseline or is/are no longer of clinical significance. Discontinuation of study drug will only occur if mandated by safety events as defined below:

Approved by: [name]	Protocol No. SARO.17.009 Version No.: 5.0
------------------------------------	--

 Zydus Discovery DMCC	CLINICAL TRIAL PROTOCOL Saroglitazar Magnesium – Phase 2A SARO.17.009	Confidential Page 44 of 82
--	---	-------------------------------

- Discontinue any patient with an adverse event of Common Terminology Criteria for Adverse Event (CTCAE) grade 3 or higher that is possible or probable drug related and discontinue any patient with an AE of CTCAE grade 4 or higher regardless of attribution to drug.
- Serious AE that may be related to the drug and warrant discontinuation as per discretion of the PI.
- In the opinion of the PI, continuation of study drug poses a health risk to the patient.
- Evidence of drug induced liver injury requiring study drug discontinuation as shown in the algorithm below.
- The second LFTs [AST, ALT, ALP, GGT, serum protein, albumin and total bilirubin (with conjugated bilirubin)] values during the Screening Phase (those obtained at Visit 2) will be considered as baseline for the safety assessment.
 - If patients with abnormal baseline liver indices develop elevations of AST or ALT greater than 2 times baseline or total bilirubin greater than 1.5 X baseline values (BL) while on study, testing should be repeated within 48-72 hours. If there are persistent elevations in ALT or AST greater than 2 X baseline or TB greater than 1.5 X baseline values, then close observation (see DILI Guidance for definition, testing and physical examination 2-3 times per week) should be initiated or drug should be discontinued.
 - A decision to discontinue or temporarily interrupt a study drug should be considered based on factors that include how much higher baseline ALT and AST were relative to the upper limit of normal (ULN) and how much the on study ALT and AST levels have increased relative to baseline, in addition to whether there is concomitant elevation of bilirubin or INR.

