 - The criteria for discontinuing or temporarily interrupting study drug are as follows:
 - When the baseline values were ≥ 1.5 X ULN but < 5 X ULN, discontinue if ALT or AST increases to > 3 X baseline.
 - Discontinue if ALT or AST increase > 2 X baseline and the increase is accompanied by a concomitant TBL increase to > 2 X baseline or the INR concomitantly increases by > 0.2 .
 - Discontinue and evaluate any patient with elevations of ALT/AST if sign or symptoms of right upper quadrant pain, abdominal pain, anorexia, nausea, vomiting fever, eosinophilia and/or rash are present.
 - If a patient lives in a remote area, they can be tested locally and the results be communicated to the investigator site promptly.

 Zydus Discovery DMCC	CLINICAL TRIAL PROTOCOL Saroglitazar Magnesium – Phase 2A SARO.17.009	Confidential Page 45 of 82
---	---	-------------------------------

- Total CK > 5X ULN
- Amylase or lipase > ULN
- eGFR < 60 ml/min/1.73 m² and where the value is reconfirmed after 24 hours. Additionally, any subject who requires renal replacement therapy should also be discontinued from drug.
- Complete Blood Counts: Hemoglobin < 10 g/dL or HCT < 30%; platelets < 100,000/microL; WBC < 4 x 10⁹/L.

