6.2.1 Abnormal Laboratory Findings

In addition, a clinically significant value outside the normal or reference range in a routine safety assessment, such as clinical laboratory, vital signs or ECGs, may signify an adverse finding. Additional examinations or repetition of test will be performed as medically indicated. If the Investigator considers the abnormality as of major relevance, he/she should also record this as an AE. If the findings contribute to a clinical diagnosis (e.g. hepatitis in case of increased liver enzymes), then this diagnosis should be recorded as AE. The criteria for determining whether an abnormal objective test finding should be reported as an AE are as follows:

1. Test result is associated with accompanying symptoms, and/or
2. Test result requires additional diagnostic testing or medical/surgical intervention, and/or
3. Test result leads to change in study dosing or discontinuation from the study, significant additional concomitant drug treatment or other therapy, and/or
4. Test result leads to any of the outcomes included in the definition of SAE, and/or
5. Test result is considered to be an AE by the Investigator.

For any abnormal test result that meets one of the above conditions except for the last condition, the Investigator will provide a justification for not reporting the abnormal test finding as an AE. Each AE shall be evaluated for the severity, duration, resolution, action taken and its association with the study treatment. The study participant may be withdrawn or terminated from the study depending on the seriousness of the adverse effects.

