9.8 Safety Analysis

9.8.1 Adverse Events

The applicable definition of an Adverse Event (AE) is any unfavorable or unintended sign, symptom or disease temporally associated with the use of study drug whether or not considered related to study drug, as per the study protocol. Treatment-emergent AEs are defined as any AE that started after the first dose of study drug or started before the first dose but increased in severity or frequency after administration of the initial dose of study drug. The period for treatment-emergent AE analysis starts from the first exposure to the study drug until the participant exits the study.

All the AEs, serious adverse events (SAEs), treatment emergent adverse event (TEAEs) and expected adverse event reported throughout the study, shall be coded and classified according to the standards of latest version of MedDRA (Medical Dictionary for Regulatory Activities) and grouped by preferred term (PT) and system organ class (SOC).

All adverse events for each participant, including the same event on several occasions should be listed for safety population giving both preferred term and original term used by the investigator.

The summary of frequency counts of the number of adverse events (E), and the number of participants with adverse events (n), and the percentages (%) for the number of participants with adverse events will be presented for treatment groups and for overall. For the summaries which count the number of participants, if a participant has more than one TEAE the participant will be counted only once in accordance with SOC and PT. When AEs occur more than once for a participant, the maximal severity (Maximum severity between severity and CTCAE Grade will be considered) and the strongest relationship to the treatment group will be counted. Safety analysis population will be used for adverse events summary tables.

In addition to an overall presentation of all TEAEs, reports will be generated for special classes of TEAEs as follows:

- Overall Summary of AEs
- TEAEs by SOC and PT
- Serious TEAEs by SOC and PT
- TEAEs leading to death by SOC and PT
- TEAEs leading to permanent discontinuation by SOC and PT
- TEAEs by SOC, PT and by Strongest Relationship to Study Drug
- TEAEs by SOC, PT and by Maximum Severity

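### A laboratory result that stops study drug under Protocol 4.5 can be recorded as an SAE, an AE or neither, and no SAP table counts such stops independently of that choice

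*Protocol*

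**What the plan says.** Protocol 4.5 opens its list of individual stopping criteria with "The following clinical events warrant discontinuation of study drug". Several items are purely laboratory limits: total CK, "Amylase or lipase > ULN", reconfirmed low eGFR, blood-count limits, and ALT/AST multiples of baseline.

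Protocol 9.4.2 widens seriousness beyond the usual outcomes: "Serious AEs also include events that are medically significant in the PI's judgment". It continues with its example, "including medically significant laboratory abnormalities, such as those that warrant stopping study drug for individual patients as specified in Section 4.5". The next sentence adds that such events generally need intervention.

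Protocol 6.2.1 lists five conditions under which an abnormal test is to be reported as an AE. Condition 3 is "Test result leads to change in study dosing or discontinuation from the study". Condition 4 is "Test result leads to any of the outcomes included in the definition of SAE". Condition 5 is the investigator's own view that the result is an AE. For a result meeting any condition but the fifth, "the Investigator will provide a justification for not reporting the abnormal test finding as an AE".

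Protocol 4.4.1 requires an AE form when a patient discontinues because of an AE. It lists the safety reasons of 4.5 separately from a serious or intolerable AE.

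SAP 9.8.1 plans a table of serious TEAEs and one of "TEAEs leading to permanent discontinuation by SOC and PT". Both are built from reported events. SAP 9.8.2 gives descriptive summaries, a normal-range shift from baseline to the last visit, and threshold counts for liver tests.

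**The concern.** The class of results that 9.4.2 holds up as its example of an SAE is one that 6.2.1 allows to go without any AE record. Neither section refers to the other.

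The frequency and severity of AEs and SAEs come first in the protocol's safety criteria, and drop-outs due to AEs are recorded with them. If two sites can classify an identical laboratory stop differently and both comply with the protocol, these counts partly reflect which section the site applied. The classification also decides whether 24-hour reporting applies (9.4.2.1) and whether the event can count towards the study-termination conditions in 4.6, which are expressed as numbers of patients with graded, related AEs. SAP 7.3 closes recruitment at 60, about 30 per arm, so a few cases are visible in any of these tables.

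**Working it through.** The plan states no figure for this point, so the check is a comparison of sections, followed by an illustration of size.

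**Step 1: trace one result.** Take a symptom-free lipase just above ULN at Week 8.

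- 4.5: study drug is to be discontinued.
- 9.4.2: the result belongs to the group named as the example of a medically significant laboratory abnormality. It is an SAE if the investigator judges it so.
- 6.2.1, condition 3: stopping drug is a change in dosing, so the result meets a criterion for an AE.
- 6.2.1, closing paragraph: condition 3 is not the last condition, so the result may go unreported with a written justification.
- 4.4.1: the AE form is conditional on the discontinuation already being attributed to an AE, so it does not decide the question.

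SAE, AE and no AE record are all reachable within the text.

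**Step 2: see whether the SAP recovers the case another way.**

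- Liver tests: largely yes. For women with baseline ALT or AST of at least 1.5 x ULN, SAP 9.8.2 counts values above 3 x baseline, and values above 2 x baseline with a bilirubin or INR rise. These are close to the 4.5 limits, although the SAP refers bilirubin to ULN where 4.5 refers it to baseline.
- CK, amylase/lipase, eGFR and blood counts: there are only descriptive summaries and the shift to the last visit. Because 4.5 has a stopped patient followed until the value resolves, a Week 8 excursion can be normal again by the last visit and show no shift.
- Protocol 8.4.3 plans frequencies of abnormal values by visit. That would show a lipase above ULN, but it does not use the CK (5 x ULN) or platelet (100,000/microL) stopping limits and does not count stops.
- Disposition (SAP 9.1): this gives reasons for leaving the study. Section 4.5 stops drug while follow-up continues, so a drug stop need not appear there.

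**Step 3: plausibility.** Four stopping limits coincide with entry limits in Protocol 4.3: amylase/lipase above ULN, WBC below 4 x 10^9/L, hemoglobin below 10 g/dL and eGFR below 60. A woman admitted near a limit can cross it with a small change.

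**Step 4: illustrative size.** Assume that a proportion p of 60 women meet a 4.5 laboratory limit. Expected number = 60p; chance of at least one = 1 - (1 - p)^60.

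| Assumed p | Expected women | Chance of at least one |
|---|---|---|
| 2% | 1.2 | 0.70 |
| 5% | 3 | 0.95 |
| 10% | 6 | 0.998 |
| 15% | 9 | >0.999 |

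With six laboratory stops and one other SAE, suppose k of the six are classified as serious. The SAE rate is (1 + k)/60:

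- k = 0: 1/60 = 1.7%
- k = 3: 4/60 = 6.7%
- k = 6: 7/60 = 11.7%

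The count of women with an AE leading to discontinuation can likewise move by 0 to 6.

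**The case against.** **Seriousness is gated.** Section 9.4.2 rests on the investigator's judgment and says that medically significant events generally need intervention. A reader might infer that every 4.5 laboratory stop is automatically an SAE, or that the SAE table will fill with isolated enzyme values. The text does not say either. This stands, but the gate is also what lets sites differ.

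**The sections can be read together.** Reporting is the default in 6.2.1. An investigator who finds a result medically significant has arguably met condition 5, where no exemption exists. That holds for one investigator reasoning consistently. It does not make two investigators agree, and the exemption still names conditions 3 and 4 as eligible.

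**There is central review.** Under 9.4.2.1 the sponsor or CRO evaluates seriousness. This applies to SAE reports received; a result never reported does not reach it. Details are deferred to a safety management plan that is not among the documents and may already settle the matter.

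**The SAP is not silent.** A reader might infer that it tabulates no 4.5 threshold. That is wrong for the liver limits, as shown above. The gap is confined to the non-liver limits and to drug stops.

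**No treatment bias is shown.** Allocation is double-blind and both arms follow the same rules. A reader might infer that the comparison between arms is distorted, or that a few cases dominate the safety result. The documents support neither. What is exposed is the level of the counts and their comparability between sites.

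**Conclusion.** The inconsistency is in the current text. Sections 9.4.2, 6.2.1 and 4.4.1 leave a 4.5 laboratory stop open to three classifications, and the serious and discontinuation TEAE counts in SAP 9.8.1 inherit that choice. The laboratory values themselves stay in the database, so no record means no AE record rather than lost data.

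The size is unknown. The 2% to 15% range is an assumption. The span from 1.7% to 11.7% also assumes six stops and one other SAE, pools the arms, and reaches its ends only if all six are classified the same way. It shows how far the count could move and does not predict it. The conclusion assumes that the safety management plan does not already impose one rule.

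This is a modest defect, worth correcting because the remedy is cheap and the sample is small. It implies nothing about whether any stopping limit is right.

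**What to change.** 1. **Protocol or safety-plan clarification.** Reconcile 6.2.1 with 9.4.2. A laboratory result that leads to stopping study drug is always recorded as an AE, with no exemption for conditions 3 and 4, and its seriousness is decided by one rule stated in both sections. No stopping threshold changes.

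2. **SAP 9.8.** With recruitment closed at 60, new wording cannot repair events already recorded, so this step carries most of the value. Add one table by arm, built from laboratory, exposure and disposition data whatever the AE classification, giving:
   - women who crossed each non-liver 4.5 laboratory limit;
   - women whose drug was stopped for any 4.5 laboratory limit;
   - as a separate line, SAEs that rest solely on a 4.5 laboratory stop.

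   If the eCRF holds no reason for stopping drug, state before unblinding how a stop is linked to a laboratory result. Identify the SAEs for the separate line by blinded review before database lock.

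**Cost:** one more table from data already collected, a few more AE records, and SAE counts shown on two lines.
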